### 6.2.4 Subgroup analyses

We will perform subgroup analyses according to the following characteristics.

Table 3: Derivation of subgroups

Subgroup	eCRF sheet	Variable	Categorization
Age: 60-80 years old	Baseline form	age	age>=60 AND age<=80
Age: >80 years old	Baseline form	age	age>80
Sex: Female	Baseline form	sex	sex==1
Sex: Male	Baseline form	sex	sex==2
Length of stay below median	Discharge data form	discharge_date, start_date	generate los = discharge_date - start_date + 1 summarize los los < r(median)
Length of stay above median			summarize los los >= r(median)
Baseline ADL below median			
Baseline ADL above median			
Baseline IADL below median			
Baseline IADL above median			

Subgroup	eCRF sheet	Variable	Categorization
Number of comorbidities below median			
Number of comorbidities above median			

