## 2. Study Methods

### 2.1 Trial design

The INTOMOB RCT is a multicenter, cluster, randomized, controlled, superiority trial conducted in three hospitals in Switzerland, with a 180-day follow-up. The intervention is partially blinded. Outcome assessment and data analysis are blinded. Hospital wards are randomized in a 1:1 ratio to either intervention or control arm. Patients admitted to an intervention ward receive the intervention, while patients admitted to a control ward receive standard of care.

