### 2.3 Sample size

See section 5.1 of the protocol, under “Sample size calculation for the RCT”. The calculated sample size includes a total of 274 patients (137 in each arm, and in 12 clusters in total).

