## 4. Statistical Principles

### 4.1 Confidence intervals and *P* values

All effect measures will be accompanied by a two-sided 95% confidence interval. All applicable statistical tests will be two-sided and will be performed using a 5% significance level.

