## 6.2 Analysis methods

### 6.2.1 Primary analysis

The primary analysis will be an intention-to-treat analysis to compare the life-space assessment (LSA) between intervention and control groups at D30. LSA will be analyzed using GEEs with Gaussian distribution, exchangeable correlation structure and robust standard errors with small sample correction. This model accounts for the cluster design as well as for the small number of clusters and will be adjusted for the baseline LSA. The absolute difference between intervention group and control group will be presented with a 95% confidence interval (CI).

Continuous secondary outcomes will be evaluated likewise, adjusting for the baseline value if applicable. If outcome measures are non-normally distributed, we will apply an adequate distribution in GEE (e.g., gamma) or log-transform the outcome measure before analysis. Absolute differences between intervention group and control group will be presented with a 95% CI.

Binary outcomes will be analyzed using a GEE with a binomial distribution, a logit link, an exchangeable correlation structure and robust standard errors. Relative differences between groups will be presented as odds ratio with 95% CI.

Count outcomes will be analyzed using a GEE with a negative binomial distribution, a log link, an exchangeable correlation structure and robust standard errors. Relative differences between groups will be presented as rate ratio with 95% CI.

Time-to-event outcomes will be analyzed using a Cox regression model. To account for clustering, we will use shared frailties for clusters as well as cluster robust standard errors. Relative differences between groups will be presented as hazard ratio with 95% CI.

Categorical outcomes (discharge destination) will be analyzed using multinomial logistic regression with robust standard errors to account for clustering. Relative differences between groups will be presented as rate ratios with 95% CI.

Readmissions and emergency room visits will be analyzed as time-to-event outcomes, except if we notice that those outcomes often happen multiple times. In such case, we will analyze them as count outcomes.

Mortality and time to new institutionalization will be analyzed as time-to-event.

Falls will be analyzed as binary outcomes. If we notice that this outcome often happens multiple times, we will analyze it as a count outcome.

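### The subgroup section lists 12 subsets but names no test of whether the intervention effect differs between the two levels of a factor

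*SAP*

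**What the plan says.** SAP section 6.2.4 consists of one sentence, "We will perform subgroup analyses according to the following characteristics", and Table 3. The table has 12 rows: two levels each of age, sex, length of stay, baseline ADL, baseline IADL and number of comorbidities. Where a derivation is given, each level has its own filter, for example "age>=60 AND age<=80" for the younger age group. Length of stay, ADL, IADL and comorbidities are divided at the median. The section names no model, outcome, interaction term or rule of interpretation.

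The other analysis sections do not fill the gap. Section 6.2.1 gives the primary model: "LSA will be analyzed using GEEs with Gaussian distribution, exchangeable correlation structure and robust standard errors with small sample correction", adjusted for baseline life-space score (LSA). Section 6.2.3 adds mixed models and further covariates, and section 6.2.5 is marked not applicable. None contains an arm-by-subgroup term. Section 4.1 sets the general rule: "All applicable statistical tests will be two-sided and will be performed using a 5% significance level".

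**The concern.** A subgroup analysis asks whether the effect of the intervention depends on a patient characteristic. Two separate results, one per level, do not answer that. One level can reach significance and the other miss it by chance alone when the true effect is the same in both. The direct answer is the estimated difference between the two effects, with its own interval and test, and the plan does not ask for it.

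At stake is how the secondary findings are read, for instance a statement that the intervention works in patients up to 80 but not in older ones. The primary analysis is not affected.

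**Working it through.** **Inputs from the SAP.** 274 patients, 137 per arm, 12 wards (section 2.3); wards randomized 1:1 (section 2.1); two-sided 5% level (section 4.1); six factors with two levels each (Table 3). The arithmetic agrees: 2 × 137 = 274. The figure of 274 cannot be rebuilt from the SAP, because section 2.3 leaves the calculation to protocol section 5.1.

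**Assumptions.** Overall power 80–90%; ICC 0–0.05; splits of 50/50 or 30/70. Baseline adjustment and the small-sample correction are left out.

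**Step 1: effect that gives the assumed power.** With m = 274/12 = 22.83 patients per ward and DEFF = 1 + (m − 1) × ICC, the standardized effect is d = (1.960 + z_power) × √(2 × DEFF/137). At 80% power and ICC 0, d = 2.802 × √(2/137) = 0.338.

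**Step 2: power within one level.** In a 50/50 split each level has 68.5 patients per arm. The expected z is 0.338/√(2/68.5) = 1.98, so power is 50.8%.

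**Step 3: chance that exactly one level is significant although the effect is uniform.** P = p1(1 − p2) + p2(1 − p1) = 2 × 0.508 × 0.492 = 50.0%. The design effect is recomputed for the smaller ward size in each level.

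| Overall power | ICC | 50/50 split | 30/70 split |
|---|---|---|---|
| 80% | 0 | 50.0% | 54.9% |
| 80% | 0.01 | 49.5% | 54.3% |
| 80% | 0.05 | 46.0% | 50.1% |
| 90% | 0 | 46.6% | 54.0% |
| 90% | 0.01 | 44.0% | 51.3% |
| 90% | 0.05 | 35.8% | 42.0% |

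The range is 35.8% to 54.9%.

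**Step 4: shared ward effects.** The formula in step 3 treats the two levels as independent. When ICC exceeds 0 they share wards, so their estimates are positively correlated. At ICC 0.05 and a 50/50 split, the variance of each estimate is 2 × 1.521/68.5 = 0.0444 and the covariance is 2 × 0.05/6 = 0.0167, a correlation of 0.375. Under a bivariate normal distribution with that correlation, the lowest table entry falls from 35.8% to 28.0%, and the 80% power entry from 46.0% to 35.0%. The entries at ICC 0 do not change.

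**Step 5: six factors together.** In 5,000 simulated trials per setting (50/50 splits, no clustering, factors uncorrelated or with latent correlation 0.5), at least one factor showed the discordant pattern in 84.5–86.6% of trials at 80% power and in 80.5–83.3% at 90% power.

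**Step 6: the same uniform effect with an interaction test.** The false-difference rate is 5% per factor by construction (simulated 4.9–5.3%). For at least one of six independent factors it is 1 − 0.95^6 = 26.5% (simulated 23–28%). For the five baseline factors alone it is 1 − 0.95^5 = 22.6%.

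**Step 7: what the interaction test can detect.** With a 50/50 split and ICC 0, the standard error of the difference between levels is twice that of the overall effect. An interaction as large as the overall effect has expected z = 2.802/2 = 1.401, hence power Φ(1.401 − 1.960) = 29%. If the trial has 90% power, Φ(3.242/2 − 1.960) = 37%.

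**The case against.** The strongest reply is that the SAP states no subgroup procedure at all. Table 3 is headed as a derivation table, as Table 2 is for outcomes, and the same categories would be coded for an interaction model. A reader might infer that 12 separate refits are prescribed; the text does not say so. This stands, and it limits the point to the absence of a test. It does not remove the point, because the analysis plan is where such a test belongs, and section 6.2.4, unlike section 2.3, does not refer to the protocol.

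Second, the harm requires someone to compare significance between levels. No section orders that comparison, and section 4.1 requires an interval with every effect measure. So false subgroup claims could follow; they will not necessarily.

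Third, a reader might compute 1 − 0.95^12 = 46% as the chance of a false positive somewhere among 12 tests when there is no effect. That needs 12 independent tests, whereas the rows are six partitions of the same patients. Simulation with that structure gives about 30%.

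Fourth, median splits are a common, pre-specified choice. They lose information, but a continuous modifier imposes a linear interaction on bounded scores. Preferring one over the other is largely judgement.

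**Conclusion.** The point holds as a cheap improvement to a secondary analysis. As written, section 6.2.4 gives effects within subsets and no test of a difference between them. If significance were compared between levels, a uniform effect would look like a subgroup difference for roughly 36–55% of factors with the levels treated as independent, and for as few as about 28% once shared ward effects are counted. An interaction test brings this to about 5% per factor. The figures rest on assumed power, ICC and split sizes; the contrast with 5% is large throughout the range.

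The document does not support saying that the plan mandates separate refits, that it will generate false claims, or that the median cuts are an error.

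**What to change.** In section 6.2.4, state that for each baseline factor (age, sex, ADL, IADL, number of comorbidities) the primary GEE will be fitted in the full analysis set with an arm-by-factor interaction and the same small-sample-corrected robust standard errors. Report the interaction estimate with its 95% interval and p-value. Show level-specific estimates with intervals but without p-values, and label all subgroup results exploratory. Optionally, add ADL, IADL and comorbidity count as continuous modifiers beside the median split.

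Treat length of stay separately. It is measured after randomization and the intervention could influence it, so an interaction term does not make it a valid subgroup factor; label it descriptive only.

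The cost is a few sentences in the SAP and no new data. The drawback is the low power shown in step 7, so a non-significant interaction must not be read as proof of a uniform effect.

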### 2.2 Randomization

Since the INTOMOB trial is a cluster RCT, only the wards (i.e., the clusters) have to be randomized. Ward randomization was done in a 1:1 ratio and generated shortly before start of the RCT by a statistician from CTU Bern (University of Bern, [name]). The statistician only received identifiers and not the actual names of the hospitals and wards in order to stay blind. Randomization was blocked with block size two and stratified by hospital to have the same ratio of intervention and control wards in each study center. Randomization was also stratified by ward size (<30 beds or  $\geq$ 30 beds). HCPs working on an intervention ward and participating patients admitted to an intervention ward receive the INTOMOB intervention. HCPs working on a control ward and participating patients admitted to a control ward receive the control procedure.

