### 5.2 Eligibility

The inclusion criteria are:

- Admission to a general internal medicine (GIM) ward of a participating hospital,
- Age  $\geq$  60 years,
- Being ambulatory during the 2 weeks before admission (self-report),
- Living in the community (not in a nursing home or another institution) for at least the last 30 days prior to admission,
- Ability to understand French or German,
- Planned length of stay at least 3 days after enrollment.

The exclusion criteria are:

- Medical contraindication to walk (e.g., wound not allowing loading weight),
- Wheelchair-bound,
- End-of-life,
- Severe psychiatric disorder (severe depression, schizophrenia, psychosis),
- Delirium (according to the Confusion Assessment Method [CAM]),
- Cognitive impairment making impossible to use study material (i.e., to implement the intervention) and to understand and sign informed consent, based on clinical judgement, except if a proxy can be actively involved in the study and provides consent,
- Severe visual impairment.

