# **7. Changes from the Protocol**

The SAP is consistent with principle features of the statistical methods described in the protocol. Any deviation from the protocol is detailed hereunder with reason.

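### Table 3 forms two subgroups from observed length of stay, which is known only after exposure to the ward intervention, so both subgroup effects can be biased

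*SAP*

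**What the plan says.** Table 3 in SAP section 6.2.4 lists "Length of stay below median" and "Length of stay above median" as subgroups. The source is the Discharge data form and the derivation is "generate los = discharge_date - start_date + 1". The lower group lies strictly below the median and the upper group at or above it; the cut is not arm-specific.

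Of the other factors in the table, age and sex come from the Baseline form, and ADL and IADL are labelled baseline. The comorbidity rows give neither source nor timing. Length of stay is therefore the only factor shown to come from a post-baseline form.

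On timing, section 2.2 says the ward allocation was "generated shortly before start of the RCT". Section 2.1 says "Patients admitted to an intervention ward receive the intervention", and section 2.7 puts discharge at visit 2, after visit 1 on day 0. Section 6.2.4 has no caveat on these two rows and no method for a subgroup variable observed after exposure.

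**The concern.** A subgroup comparison keeps the protection of randomisation only if membership cannot be altered by the allocated treatment. Observed stay does not meet that requirement, because it ends at discharge, after the patient has been on an intervention or control ward.

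Suppose the intervention shortens stay. Some intervention patients who would have fallen in the long-stay half under control now fall in the short-stay half. If longer stay goes with worse prognosis, these patients lower the average prognosis of the intervention arm in the short-stay half. Their departure also leaves the intervention arm of the long-stay half with the worse remainder. Both halves are then shifted in the same direction against the intervention, although the unsplit comparison is correct.

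At stake is how the two length-of-stay results are read: neither could be taken as the effect in short-stay or long-stay patients, and the reported confidence intervals would not show the problem. The primary analysis does not use this split.

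**Working it through.** The plan gives no figure for this subgroup, so there is nothing to reproduce. The calculation illustrates the possible size.

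**Inputs from the SAP:** split at a common median (Table 3); 137 patients per arm (section 2.3), so about 137/2 = 68.5 per arm in each half; the LSA model "will be adjusted for the baseline LSA" (section 6.2.1).

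**Assumptions, not in the SAP:** LSA SD 28; true effect 0; stay in SD units = U - s × arm, with U standard normal and s = 0.2, 0.3 or 0.5; correlation r(Y,U) of day-30 LSA with stay = -0.4. For the adjusted model, the correlation r(Y,B) of baseline with day-30 LSA is 0.5, 0.6 or 0.7, paired with a correlation r(B,U) of baseline LSA with stay of -0.30, -0.35 or -0.40.

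**Step 1, imbalance within each half.** The pooled median lies at -s/2. The lower half therefore holds control patients with U < -s/2 and intervention patients with U < s/2. The arm difference in mean U (intervention minus control) is

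d = φ(s/2) × [1/(1 - Φ(s/2)) - 1/Φ(s/2)],

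and by symmetry it is the same in the upper half. For s = 0.3: 0.3945 × (1/0.4404 - 1/0.5596) = 0.191. For s = 0.2 and 0.5, d = 0.127 and 0.318.

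**Step 2, unadjusted bias** = r(Y,U) × d × 28. For s = 0.3: -0.4 × 0.191 × 28 = -2.1 points. For s = 0.2 and 0.5: -1.4 and -3.6.

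**Step 3, bias after adjustment for baseline LSA** = [r(Y,U) - b × r(B,U)] × d × 28. Here b is the slope of day-30 on baseline LSA within arm and half:

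b = [r(Y,B) - k × r(Y,U) × r(B,U)] / [1 - k × r(B,U)²], with k = φ(s/2)² / [Φ(s/2)(1 - Φ(s/2))].

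For s = 0.3, r(Y,B) = 0.5 and r(B,U) = -0.30: k = 0.631 and b = (0.5 - 0.631 × 0.12)/(1 - 0.631 × 0.09) = 0.450. The bias is (-0.4 + 0.450 × 0.30) × 0.191 × 28 = -1.4 points.

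| r(Y,B), r(B,U) | s = 0.2 | s = 0.3 | s = 0.5 |
|---|---|---|---|
| unadjusted | -1.4 | -2.1 | -3.6 |
| 0.5, -0.30 | -0.9 | -1.4 | -2.4 |
| 0.6, -0.35 | -0.7 | -1.1 | -1.8 |
| 0.7, -0.40 | -0.5 | -0.7 | -1.2 |

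A simulation of 4,000,000 patients, with regression on arm and baseline LSA, agreed within 0.1 point (for s = 0.3 and the second row, -1.39 and -1.41 in the two halves). It gave an overall effect of 0.0.

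**Step 4, sensitivity.** With a true effect of +5, the adjusted estimates in both halves lie between 5 - 2.4 = 2.6 and 5 - 0.5 = 4.5, so the sign does not reverse. With r(Y,U) = -0.2 and the other inputs unchanged, the adjusted bias runs from -0.5 to +0.8, so its direction is not fixed. It is zero if s = 0, or if stay is unrelated to both baseline and day-30 LSA.

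**Step 5, scale.** The standard error per half is 28 × √(1 - r²) × √(2/68.5). This gives 4.8 points unadjusted (r = 0) and 4.1, 3.8 and 3.4 for r = 0.5, 0.6 and 0.7, before any inflation for clustering. Every bias shown is below one standard error.

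**Second model.** A separate simulation used other assumptions: LSA SD 25; log-normal stay, rounded, with control median 8 days and log-SD 0.5; LSA correlated -0.3 or -0.5 with log stay; no baseline adjustment; true effect 0. Stay 10% shorter gave -0.9/-1.0 points (below/above median) at -0.3 and -1.7/-1.6 at -0.5. Stay 20% shorter gave -2.1/-2.0 and -3.8/-3.3. With no effect on stay, both halves were within 0.1 of zero, and the overall difference was within 0.06 of zero throughout.

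**The case against.** The strongest reply is that nothing in the SAP shows that the intervention changes stay. Length of stay is neither an objective nor an outcome, and the shifts, correlations and SD above are all assumed. Under the planned baseline-LSA adjustment the illustrated bias is small against the noise, and at a weak correlation it has no fixed sign. This stands, and it limits the weight of the point. It does not make the subgroup valid: the SAP tests discharge destination and in-hospital outcomes such as delirium for superiority, so an effect on the course of the stay cannot be ruled out in advance.

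Section 6.2.3 also plans a sensitivity analysis with further covariates (age, sex, body mass index, functional limitations, fear of falling, muscle strength). It could reduce the bias further, but it does not name the subgroups and cannot remove selection through unmeasured prognosis.

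In a cluster trial every patient variable, even age, is recorded after the wards were randomised. That is correct, so the feature that separates stay from the other factors is exposure to the intervention. The SAP also leaves the start date undefined. If it is the admission date, part of the stay may precede enrolment, but the total still depends on discharge.

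Finally, the protocol may prespecify this subgroup or call it exploratory. Prespecification would not turn observed stay into a baseline factor, and Table 3 lists it beside age and sex without distinction.

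**Conclusion.** The concern holds. It is certain from the text that the split variable is observed after exposure and that the SAP neither labels nor handles it as such. Material bias in this trial is not established: it needs both an effect of the intervention on stay and a link between stay and LSA, and the SAP shows neither. Under the stated assumptions the adjusted bias is about half a point to two and a half points in each half, with the overall effect correctly estimated. The matter is confined to the two length-of-stay rows. It should be corrected because the change is nearly free and the results could otherwise be misread.

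**What to change.** Remove the two length-of-stay rows as treatment-effect subgroups, or replace them with a factor fixed at enrolment. Section 5.2 requires "Planned length of stay at least 3 days after enrollment", so planned stay is already judged at that point and could be used if it was recorded in days. Baseline DEMMI (Table 1) could serve as a marker of severity, though not of exposure time.

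If the rows are kept, state in section 6.2.4 that they are descriptive and do not estimate the effect in short-stay or long-stay patients. In every case report length of stay by arm, so that readers can judge whether the intervention changed it.

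If the protocol prespecifies this subgroup, record the change in section 7, which says "Any deviation from the protocol is detailed hereunder with reason".

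The cost is two table rows or one label, plus possibly a short note in section 7. Removal or relabelling needs no new data; replacement by planned stay depends on whether it was recorded.

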### **6.2.5 Additional analyses**

Not applicable

### **6.2.6 Assessment of statistical assumptions**

Model residuals will be inspected visually for normality using QQ-plots (Quantile-Quantile-plots).

### **6.3 Interim analyses**

Not applicable.

### **6.4 Missing data**

If the primary outcome is missing in more than 5% of patients, we will employ multiple imputation in the primary analysis and additionally perform an available case analysis as sensitivity analysis disregarding missing data.

Multiple imputation will be via chained equations assuming missing data to be missing at random (MAR). Where endpoints are missing, each will be imputed separately to ensure robust imputation models. We will use all baseline variables (see table 1 in section 5.4) and outcome measures at all time points as predictors in the imputation models. Indicators for intervention and treatment will be included in the imputation model(s). Variables with more than 50% missing values will not be used for the imputation model. Binary variables with a frequency of less than 5% in one category will be omitted from the predictors, levels of categorical variables with a frequency of less than 5% in one category will be combined with another level in a sensible way. Continuous variables will be log-transformed if it improves normality (checked by Shapiro-Wilks test and QQ plots). If predictors are too highly correlated among each other, we will only consider the predictor which is more strongly correlated with the outcome. We will impute values using predictive mean matching for continuous and ordinal variables, logistic regression for binary variables, and a multinomial regression model for categorical variables with more than two levels. In total, fifty imputed data sets will be generated, which will be analyzed as described using Rubin's rules (Rubin 1987).

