### 4.3 Estimands

#### 4.3.1 Primary outcome on the FAS

**Outcome of interest:** life-space assessment at 30 (+/-5) days

**Patient-set of interest:** full analysis set

**Handling of intercurrent events:** if the primary outcome is missing in more than 5% of patients, we will employ multiple imputation in the primary analysis and additionally perform an available case analysis as sensitivity analysis disregarding missing data.

**Population-level summary measure of outcome:** absolute difference with 95% confidence interval, computed using generalized estimated equations (GEEs) with Gaussian distribution, exchangeable correlation structure and robust standard errors with small sample correction.

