### 6.2.3 Sensitivity analyses

We will use generalized linear mixed-effects models instead of GEEs to account for clustering. For outcomes measured at D30 and D180, we will use a repeated-measures mixed-effects model. Should a GEE model not converge, we will use a mixed-effects model for that specific outcome as the primary analysis approach.

Because cluster randomization may lack the excellent balancing in characteristics between groups seen in individual-level randomization, we will adjust each model for additional pre-defined patient-level variables (age, sex, body mass index, LSA, number of ADLs/IADLs limitations, fear of / concerns about falling and muscle strength at baseline) to account for case-mix differences between groups in a sensitivity analysis. Moreover, we will assess imbalances of patient characteristics between groups. If we observe imbalances in covariates not considered in the sensitivity analysis, we will perform additional adjustments to assess the robustness of our results.

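### No planned analysis tests departure from missing at random: the missing-data sensitivity analysis assumes more than the imputation it is meant to check

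*SAP*

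**What the plan says.** SAP section 6.4 makes the handling of a missing primary outcome conditional on the share of patients without it exceeding 5%. In that case the plan is: "we will employ multiple imputation in the primary analysis and additionally perform an available case analysis as sensitivity analysis disregarding missing data". Section 4.3.1 repeats the rule under intercurrent events ("additionally perform an available case analysis as sensitivity analysis disregarding missing data").

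On the imputation, section 6.4 states: "Multiple imputation will be via chained equations assuming missing data to be missing at random (MAR"). Its predictors are broad: "We will use all baseline variables (see table 1 in section 5.4) and outcome measures at all time points as predictors in the imputation models". Fifty imputed data sets are to be pooled with Rubin's rules.

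The primary model is a Gaussian GEE. Of it, section 6.2.1 says: "This model accounts for the cluster design as well as for the small number of clusters and will be adjusted for the baseline LSA".

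Section 6.2.3 adds other sensitivity analyses. The first changes the model type: "We will use generalized linear mixed-effects models instead of GEEs to account for clustering". A second is a longitudinal mixed model wherever an outcome is taken at both follow-up calls, and a third adjusts for further baseline covariates because of possible case-mix imbalance. None is presented as a check on missing data. Section 6.2.2 is a per-protocol analysis, and section 6.2.5 lists no additional analyses. No delta-adjusted, reference-based or tipping-point analysis appears anywhere in the SAP.

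**The concern.** A sensitivity analysis for missing data should relax the assumption that the primary analysis cannot verify. Here that assumption is MAR: given what was observed, whether the day-30 score is missing does not depend on the score itself. The outcome is a mobility score obtained by telephone, so it is reasonable to ask whether patients who are doing badly are also the ones not assessed.

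The named check does not ask this. It drops the patients with missing scores and fits the same model, which tightens the assumption. If patients doing worse than predicted are lost more often in one arm, both results move in the same direction, and their closeness could be reported as robustness.

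**Working it through.** **1. What each analysis needs in order to be valid**

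| Analysis | SAP section | Missingness may depend on |
|---|---|---|
| Available-case GEE | 4.3.1, 6.4 | arm and baseline LSA only |
| Multiple imputation, then GEE | 6.4 | these, plus the other Table 1 variables and observed outcomes at all time points |
| Mixed models, including repeated measures | 6.2.3 | model covariates and observed outcomes (likelihood-based, so MAR) |
| Any analysis allowing dependence on the unseen score | none | – |

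The first row is a special case of the second. A difference between the two points first to a fault in the available-case analysis. Agreement does not test MAR.

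**2. When the imputation applies**

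Section 2.3 gives 274 patients, 137 per arm (2 × 137 = 274). The threshold is 0.05 × 274 = 13.7, so imputation starts at 14 missing scores. At 13 or fewer, the SAP names no missing-data sensitivity analysis.

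**3. Size of a departure from MAR**

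Let f be the missing share in an arm, and delta the amount by which unseen scores fall below their MAR prediction. The bias of the estimated difference is

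f_I × delta_I − f_C × delta_C

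(I intervention, C control). This is exact for a difference in means and approximate for the baseline-adjusted GEE. With the shortfall in one arm only, the absolute shift in LSA points is:

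| Missing in that arm | delta 5 | delta 10 | delta 20 |
|---|---|---|---|
| 5% | 0.25 | 0.5 | 1.0 |
| 10% | 0.5 | 1.0 | 2.0 |
| 15% | 0.75 | 1.5 | 3.0 |
| 20% | 1.0 | 2.0 | 4.0 |

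The shares and deltas are assumptions. If f and delta are equal in the two arms, the terms cancel.

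**4. Would the planned comparison reveal it?**

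This was simulated with 137 patients per arm, 12 clusters, a true effect of 0 and 1,500 runs per scenario. Assumed, not in the SAP: a 25-point scale, ICC 0.02, and one auxiliary predictor used by the imputation but not by the analysis model. Ten imputations and a linear estimator stood in for the 50 imputations and the GEE. In the outcome-dependent scenarios, the log-odds of loss rose by 1 per SD of lower score (by 2 where marked strong). The Monte Carlo standard error was about 0.08–0.09.

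| Loss, control / intervention | Loss depends on | Available case | Imputation | Gap |
|---|---|---|---|---|
| 15% / 15% | unseen score, both arms alike | −0.01 | 0.01 | −0.02 |
| 10% / 20% | unseen score, both arms | 1.26 | 1.12 | 0.14 |
| 15% / 15% | unseen score, intervention only | 2.10 | 1.86 | 0.24 |
| 10% / 20% | unseen score, intervention only | 2.63 | 2.34 | 0.29 |
| 20% / 20% | unseen score, intervention only, strong | 4.36 | 3.89 | 0.47 |
| 10% / 20% | auxiliary (MAR), intervention only | 0.89 | −0.07 | 0.96 |
| 20% / 20% | auxiliary (MAR), intervention only, strong | 1.55 | 0.06 | 1.49 |

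Where MAR failed unequally between arms, both results were biased by 1.1 to 4.4 points but lay only 0.1 to 0.5 apart. Where MAR held through the auxiliary variable, imputation was about unbiased and the gap was larger, 0.96 to 1.49. The gap between the two analyses is therefore not a guide to whether MAR holds.

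**The case against.** Multiple imputation under MAR with an available-case comparison is a coherent, pre-specified plan. Nothing shows the primary analysis itself to be wrong. That stands, and it limits the point to the sensitivity analysis. Four stronger readings are tempting, and the SAP does not support them.

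- *The two results will coincide.* They do when the imputation sees only arm and baseline LSA: in a simulation of that kind they differed by at most 0.02 points. Section 6.4 uses far more predictors. With loss of 6% intervention and 14% control, and an auxiliary predictor correlated 0.4, 0.6 or 0.8 with the part of the score that baseline does not explain, the available-case bias was −1.40, −1.36 and −1.41. The imputation bias was −1.21, −0.92 and −0.57. Good auxiliaries thus remove part of the bias and separate the results. The gain shrinks if patients missed at day 30 also lack later data.
- *The available-case analysis is the only sensitivity analysis.* It is the only one named for missing data. The repeated-measures model in section 6.2.3 also handles missing values, using day-180 scores, but it still assumes MAR.
- *Differential loss of poorly mobile patients is to be expected.* The SAP does not document this. Homebound patients could be easier to reach by telephone, and section 6.1 provides an institutional version of the score. Section 2.8 describes the intervention as partially blinded, with blinded outcome assessment, so it cannot be called simply unblinded.
- *Outcome-dependent loss by itself biases the result.* Identical loss in both arms left the difference near 0.

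**Conclusion.** The point holds for the choice of check. When more than 5% of day-30 scores are missing, the named sensitivity analysis rests on a stronger assumption than the analysis it checks, and no other planned analysis relaxes MAR. The two results will tend to agree, though not exactly, and agreement is not evidence against outcome-dependent loss.

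The possible shift is about 0.25 to 4 LSA points on the 0–120 scale, for 5–20% missing and a 5–20 point shortfall in one arm only. It is near zero if loss and its link to outcome are alike in both arms. These sizes rest on assumed loss rates and shortfalls; the simulated figures also rest on an assumed SD, ICC and auxiliary strength. The SAP gives none of these and no minimal important difference, so the clinical weight of such a shift cannot be judged from it. This should be changed before database lock. It is not a fault in the primary analysis.

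**What to change.** In sections 4.3.1 and 6.4, replace the available-case analysis with a delta-adjusted analysis as the missing-data sensitivity analysis for the primary outcome:

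1. Take the same 50 imputed data sets. Lower the imputed day-30 LSA of patients who are alive but not assessed by 0, 5, 10, 15 and 20 points, or another range fixed in advance, with values kept at or above 0.
2. Vary the shift by arm: both arms, intervention only, control only. The control-only shift is needed because loss concentrated among controls biases the difference in the other direction.
3. Refit the primary GEE for each combination, pool with Rubin's rules, and report the estimate with its 95% CI and the combinations at which the conclusion changes.
4. Keep the available-case analysis as supplementary, and state that it does not test MAR.

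The shift covers only patients alive at day 30, so the SAP should state separately how earlier deaths enter the analysis and the imputation.

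The cost is one SAP paragraph, a short loop over existing imputations and one more table. No new data are needed.
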